Eligible subjects may enter the Extension Phase immediately following the completion of Visit 15 of the Core Study. Subjects who are eligible to participate in the Extension Phase but who do not transition to the Extension Phase on the day of Visit 15 may enter the Extension Phase any time within 4 weeks of Visit 15. All subjects who enter the Extension Phase will be treated with elenbecestat, including the subjects who received placebo during the Core Study. For all subjects, assessments performed at Visit 15 will serve as baseline values for the Extension Phase. (revised per Amendment 05)

An independent data safety monitoring board (DSMB) will convene at regular intervals to monitor the overall safety of the study and to make recommendations to the sponsor related

to study safety as appropriate. The DSMB will be asked to review the cumulative safety data, which includes measures of cognitive safety at the group level, up to the date identified to make a determination if the trial is safe to proceed unchanged or to provide recommendations to the sponsor as to how to proceed. (revised per Amendment 05) The study will proceed, including randomization of additional subjects, during DSMB safety reviews. Details will be provided in the DSMB Charter.

An overview of the study design is presented in [Figure 1](#).

[figure not shown]

Figure 1 Study Design for E2609-G000-302 (revised per Amendment 05)

Elenbecestat = Test drug, EoT = End of Treatment, PET = positron emission tomography, R = randomization.

- a: Subjects who participate in the optional longitudinal tau PET substudy will be permitted an additional window of up to 5 days (resulting in a total of up to 85 days) in order to accommodate the additional tau PET scan required to be performed during prerandomization. (revised per Amendment 04)
- b: The last day of the Core Study (Visit 15) is also the first day of the Extension Phase

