Subjects may be re-screened, if deemed appropriate by the investigator and medical monitor. Unless otherwise stated, results of the following will be valid over the timeframes stated below: (revised per Amendment 05)

- Tiers 1 to 3 Screening will be valid for 96 days from the date of assessment
- Tier 4 MRIs will be valid for 90 days from the date of assessment

- Tier 5 CSF results and amyloid PET scans will be valid for 90 days from the date of assessment, while historical amyloid PET scans will be valid for 12 months

9.1.1.1.1 TIER 1

Subject demography and medical history will be obtained before completing the following cognitive/clinical assessments: MMSE, (ISLT, CDR, and the modified Hachinski ischemic scale. The Cogstate Brief Battery (CBB) will be administered in the 20 to 30 minutes between the ISLT total recall and delayed recall tests as a common distractor task. It is recommended that the MMSE and ISLT be completed, and eligibility on these assessments confirmed, before the CDR is administered. Subjects who are considered ineligible for the study based on these assessments should not continue with the rest of the Tier 1 assessments. For any given subject, every effort should be made to ensure that the CDR rater remains unchanged throughout the study. (revised per Amendment 03)

All subjects will be confirmed as meeting the diagnostic criteria for either MCI due to AD or the early stages of mild AD, and that they do not have other medical conditions that may interfere with study participation. The diagnosis and clinical disease staging will be verified via a central review process, and adjudicated if necessary (adjudication will only occur when there is a discrepancy between the diagnosis and clinical disease staging made by the site compared to that determined by the central review process; moreover, where adjudication is required, it will be undertaken by an independent assessor(s)). Confirmation of the diagnosis and clinical disease staging by central review will not be required in order for the subject to progress to Tier 2 of the Screening Visit, but will be required before the subject progresses to Tier 4. (revised per Amendment 03)

9.1.1.1.2 TIER 2

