9.3.3 Removal of Subjects from Therapy or Assessment

The investigator may withdraw the subject from the study at any time for safety or administrative reasons. The subject may stop study drug or withdraw from the study at any time for any reason.

Absolute lymphocyte count from the hematology and differential panel will be monitored during the study. Absolute lymphocyte count will be derived from the CBC with differential representing the normal lymphocytes (with atypical lymphocytes removed and presented as a separate count if they are present) and calculated by the white blood cell count \times percentage of lymphocytes. Should a subject develop a Grade 2 or greater lymphocytopenia (less than $800/\text{mm}^3$), the ALC test should be repeated as soon as possible with the repeat blood sample drawn no later than 5 calendar days from the date of the original test result. If confirmed, study drug administration should be interrupted for a minimum period of 2 weeks and for a maximum period of 4 weeks. Restart of study drug may take place only when absolute lymphocyte count returns to greater than $800/\text{mm}^3$. Absolute lymphocyte count will be measured 4 weeks after restart of study drug. Subsequent measurements of ALC will follow the schedule of assessments (Table 5) and any results showing a Grade 2 or greater lymphocytopenia (less than $800/\text{mm}^3$) should be handled as above. If a Grade 2 or greater lymphocytopenia (less than $800/\text{mm}^3$), that is confirmed on repeat testing, occurs twice within a 6 month period, during the Core Study Treatment Period, then the subject should be discontinued permanently from the study drug. In the Extension Phase, if a confirmed Grade 2 or greater lymphocytopenia (less than $800/\text{mm}^3$) occurs twice from Visit 16 onwards during a 6-month period then the subject should also be discontinued permanently from study drug (revised per Amendments 01, 03, and 05).

Subjects who develop moderate or severe hepatic impairment (eg, Child-Pugh Class B or C) during the study must discontinue study drug. (revised per Amendments 01 and 02) Moderate or severe hepatic impairment are defined as any 2 of the following criteria: INR ≥ 1.7 ; bilirubin $\geq 1.5 \times \text{ULN}$; albumin $< \text{LLN}$; ascites or hepatic encephalopathy. Please note that a single significant abnormality could meet criteria for moderate impairment. (revised per Amendment 02)

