All AEs must be followed for 12 weeks after the subject's last dose, or until resolution, whichever comes first. Subjects who have a Grade 2 or greater lymphocytopenia (less than 800/mm³) during the Follow-up Period (ie, at either Visit 14 or Visit 15) should have ALC measured every 4 weeks until resolution or confirmation of a non drug-related cause of the lymphocytopenia. ALC will be derived from the CBC with differential representing the normal lymphocytes (with atypical lymphocytes removed and presented as a separate count if they are present) and calculated by the white blood cell count × percentage of lymphocytes. (revised per Amendment 01) All SAEs must be followed to resolution or, if resolution is unlikely, to stabilization.

Every effort must be made by the investigator to categorize each AE according to its severity and its relationship to the study treatment.

Assessing Severity of AEs

AEs will be graded on a 3-point scale (mild, moderate, severe) and reported in the detail indicated on the eCRF. The definitions are as follows:

Mild	Discomfort noticed, but no disruption of normal daily activity
Moderate	Discomfort sufficient to reduce or affect normal daily activity
Severe	Incapacitating, with inability to work or to perform normal daily activity

The criteria for assessing severity are different than those used for seriousness (see [Section 9.5.1.5.2](#) for the definition of an SAE).

Assessing Relationship to Study Treatment

Items to be considered when assessing the relationship of an AE to the study treatment are:

- Temporal relationship of the onset of the event to the initiation of the study treatment
- The course of the event, especially the effect of discontinuation of study treatment or reintroduction of study treatment, as applicable
- Whether the event is known to be associated with the study treatment or with other similar treatments
- The presence of risk factors in the study subject known to increase the occurrence of the event
- The presence of nonstudy, treatment-related factors that are known to be associated with the occurrence of the event

Classification of Causality

The relationship of each AE to the study drug will be recorded on the eCRF in response to the following question:

Is there a reasonable possibility that the study drug caused the AE?

Yes (related) A causal relationship between the study drug and the AE is a reasonable possibility.

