aPTT = activated partial thromboplastin time, CMV = cytomegalovirus, CSF = cerebrospinal fluid, HBsAg = hepatitis B surface antigen, HCVAb = hepatitis C virus antibody, HSV-1 = herpes simplex virus-1, HSV-2 = herpes simplex virus-2, INR = International Normalized Ratio, MMA = methylmalonic acid, PBMCs = peripheral blood mononuclear cells

a: ALC will be derived from the CBC with differential representing the normal lymphocytes (with atypical lymphocytes removed and presented as a separate count if they are present) and calculated by the white blood cell count × percentage of lymphocytes. (revised per Amendment 01)

Clinical laboratory tests during all phases of the study will be performed by a central laboratory. All blood and urine samples will be collected and sent to the central laboratory on the day of collection unless otherwise instructed. In cases of a safety concern, blood samples will be split (or 2 samples drawn) to allow a local laboratory analysis in addition to the central laboratory. Laboratory certification as available will be included in the final clinical study report for this study.

A laboratory abnormality may meet the criteria to qualify as an AE as described in this protocol (see [Section 9.5.1.5.1](#)) and the CRF Completion Guidelines. In these instances, the AE corresponding to the laboratory abnormality will be recorded on the Adverse Event eCRF.

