Appendix 5 Open-label Extension Phase (revised per Amendment 05)

Primary Objective

- To assess the long-term safety and tolerability of daily dosing with elenbecestat in subjects with Early Alzheimer's Disease (EAD)

Secondary Objectives

- To evaluate the long-term effects of elenbecestat on Clinical Dementia Rating –Sum Of Boxes (CDR-SB), Alzheimer's Disease Composite Score (ADCOMS), Mini Mental State Examination (MMSE), Functional Assessment Questionnaire (FAQ), Alzheimer's Disease Assessment Scale - cognitive subscale (ADAS-cog14), and ADAS-cog14 Word List (immediate recall and delayed recall)
- To evaluate the time to conversion to dementia for subjects who were not clinically staged as having dementia at Core Study baseline, based on clinical diagnosis
- To evaluate whether the treatment benefit of elenbecestat at the end of the Core Study is maintained over time in the Extension Phase

Biomarker Objectives

- To evaluate the long-term effect of elenbecestat on brain amyloid and tau levels as measured by positron emission tomography (PET) (optional substudy)
- To evaluate the long-term effect of elenbecestat on hippocampal atrophy as measured by changes in hippocampal volume using volumetric magnetic resonance imaging (vMRI)
- To evaluate the long-term effect of elenbecestat in preserving brain connectivity as measured by task-free functional magnetic resonance imaging (fMRI)
- To evaluate the long-term effect of elenbecestat on CSF t-tau, p-tau, and amyloid beta (A β) levels (optional substudy)
- To evaluate the long-term effect of elenbecestat on plasma amyloid (eg, A β (1-x)) levels
- To explore the long-term effect of elenbecestat on potential plasma and CSF biomarkers of AD (eg, neurofilament (NFL), visinin like protein 1 (VILIP1), human cartilage glycoprotein-39 (YKL-40), and neurogranin [Ng])

Exploratory Objectives

- To explore the long-term effect of elenbecestat on the initiation or dose increase of other Alzheimer's disease (AD) pharmacotherapies
- To explore the long-term effect of elenbecestat on the Neuropsychiatric Inventory (NPI)-10 and if available NPI-12

Eligibility Criteria

Subjects who do not meet all of the inclusion criteria will not be eligible to receive study drug.

Inclusion:

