1. Subjects who complete the 24-month Treatment Period and the 3-month Follow-up period (Visit 15) of the Core Study and whose Visit 15 falls within a 4-week window from the start of the Extension Phase. Subjects who discontinue study drug early are not considered to have ‘completed’ the Core Study.
2. Provide written informed consent. Subjects must, in the investigator’s judgment, have the capacity to consent (capacity to consent should be determined in accordance with applicable professional standards and local laws/regulations). In Japan, if a subject loses the capacity to consent, in the investigator's opinion during the course of the Core Study, the subject's assent should be obtained (if required in accordance with local laws, regulations, and customs) along with the written informed consent of a legal representative. (revised per Amendment 06)
3. Subjects must continue to have an identified study partner who is willing and able to provide follow-up information on the subject throughout the course of the Extension Phase.

Study Design and Plan

The Extension Phase allows eligible subjects to receive elenbecestat 50 mg for up to 24 months (2 years), or until commercial availability of elenbecestat or a lack of positive benefit-risk is determined, whichever comes first.

Subjects who are enrolled and complete the Core Study, including the 3-month follow-up period, will have the option to participate in the Extension Phase. Subjects who discontinue from study drug during the Core Study are not eligible to participate in the Extension Phase.

Eligible subjects may enter the Extension Phase immediately following the completion of Core Study Visit 15. Subjects who are eligible to participate in the Extension Phase but who do not transition to the Extension Phase on the day of Visit 15 may enter the Extension Phase any time within 4 weeks of Visit 15. For all subjects, assessments performed at Visit 15 may serve as baseline values for the Extension Phase.

Subjects may discontinue from the open-label study drug for any reason but are required to complete the Early Discontinuation (ED) Visit (within 7 days of last dose). In addition, subjects are required to discontinue the open-label study drug if any of the criteria specified in [Section 9.3.3](#) (Removal of Subjects from Therapy or Assessment) are met.

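### Appendix 5 sets no entry-specific ALC requirement: a known, unresolved count below 800/mm3 at Visit 14 or Visit 15 does not hold back the first open-label dose

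*Protocol*

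**What the plan says.** Appendix 5, Eligibility Criteria, makes open-label drug depend on three inclusion criteria (completion of the Core Study, consent, a continuing study partner): "Subjects who do not meet all of the inclusion criteria will not be eligible to receive study drug". Entry can be on the same day: "Eligible subjects may enter the Extension Phase immediately following the completion of Core Study Visit 15", or within 4 weeks of Visit 15. Footnote b to Figure 1 in Section 9.1 adds that "The last day of the Core Study (Visit 15) is also the first day of the Extension Phase". Table 5 schedules dispensing for Extension entrants under footnote dd.

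For low counts during the off-drug follow-up, the instruction in Section 9.5.1.5.1 reads: "ie, at either Visit 14 or Visit 15) should have ALC measured every 4 weeks until resolution or confirmation of a non drug-related cause". Table 5 footnote c repeats this instruction and also makes Visit 15 the Extension baseline. Neither place says what a low count means for open-label dosing.

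Section 9.3.3 holds the ALC dosing rules. On treatment, a count below 800/mm3 is repeated no later than 5 calendar days after the result and, if confirmed, drug is interrupted for 2 to 4 weeks. Then: "Restart of study drug may take place only when absolute lymphocyte count returns to greater than" 800/mm3. Permanent discontinuation follows two confirmed events within 6 months. In the Core Study these are counted during the Treatment Period. In the Extension the rule applies if such an event "occurs twice from Visit 16 onwards during a 6-month period then the subject should also be discontinued permanently from study drug".

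**The concern.** For subjects randomized to placebo, Extension Day 1 is the first exposure to elenbecestat. Section 7.1 reports some CD4 reduction at 50 to 100 mg by Day 15 of the multiple-dose study, and the study dose is 50 mg. Elsewhere the protocol treats 800/mm3 as a limit for dosing. Criterion 9 in Section 9.3.2 requires a Screening ALC not below the higher of the lower limit of normal and 800/mm3. Section 9.3.3 interrupts drug on a confirmed value below 800/mm3 and restarts it only above that level.

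At the Core-to-Extension transition no such limit is written. At stake is the safety of individual entrants, and whether sites handle the same laboratory finding consistently in a phase whose primary objective is long-term safety.

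**Working it through.** No sample size, power or error rate is involved. The check sets the rules side by side and then does day arithmetic on the Table 5 visit days: Visit 13 = Day 729, Visit 14 = Day 757, Visit 15 = Day 813.

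**Which rule acts on an ALC below 800/mm3 at Visit 14 or 15?**

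- Core Screening limit (9.3.2, criterion 9): no. It is tied to tests done during Screening.
- Interruption and restart rule (9.3.3): not before dosing. It presupposes study drug that was running and then interrupted. A subject who completed 24 months of treatment has not been interrupted.
- Core two-event rule (9.3.3): no. It is limited to the Core Treatment Period, and Visits 14 and 15 are follow-up.
- Extension two-event rule (9.3.3): no. It counts from Visit 16.
- Follow-up instruction (9.5.1.5.1; Table 5 footnote c): yes, but it asks only for repeat measurements.
- Appendix 5 inclusion criteria: no. None mentions ALC.

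Nothing in this list withholds the first open-label dose.

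**Case A, low at Visit 14.** Repeats fall on about 757 + 28 = Day 785, 785 + 28 = Day 813 (Visit 15) and 813 + 28 = Day 841 (last day of the entry window). If the Day 785 value is still low, the site arrives at Visit 15 with a known, unresolved finding and may dispense.

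**Case B, normal at Visit 14, low at Visit 15.** Visit 15 samples go to the central laboratory: "All blood and urine samples will be collected and sent to the central laboratory on the day of collection unless otherwise instructed". With same-day entry the result would normally arrive after the first dose, and 9.3.3 can then apply. If entry is deferred within the 4 weeks, the result is known before dosing and again nothing bars it.

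**Could a requirement be met with data already collected?**

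- Age of the Visit 14 result at entry on Day 813: 813 - 757 = 56 days.
- Age at the last entry day: 813 + 28 = 841; 841 - 757 = 84 days.
- Core comparator (9.1.1.1): "Tiers 1 to 3 Screening will be valid for 96 days from the date of assessment", and the Screening hematology is drawn in Tier 3. Both 56 and 84 are under 96.

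A normal Visit 14 value would therefore be no staler than what the Core Study accepts, and no new scheduled draw is needed.

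**The case against.** The best case against is that other safeguards surround this step. Anyone who discontinued study drug in the Core Study is barred from the Extension. That removes subjects with two confirmed lymphocytopenias within 6 months, and those permanently stopped for a seizure or hepatic impairment. Table 5 schedules an inclusion and exclusion review for entrants, together with safety checks such as the C-SSRS and a pregnancy test. Appendix 5 applies the 9.3.3 discontinuation criteria to open-label drug, and because Visit 15 is Extension Day 1, a low Visit 15 count can be read as triggering the 5-day repeat. Blood counts follow on Extension Days 15, 29 and 57. In addition, 9.3.3 does not stop drug on a single unconfirmed low value, so its restart rule is the strictest available comparator. Section 7.1 reports that lymphocyte effects after 14 days of dosing resolved between 6 and 21 days after the last dose, whereas Visit 14 is 28 days after it.

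Most of this stands, and it limits the point. A reader might infer that the Extension has no safety gate at all; the bar on Core discontinuers and the scheduled entry review contradict that. A reader might also infer that the prohibited-drug bans of Section 9.4.7 lapse after Visit 13, leaving 813 - 729 = 84 days uncovered. The synopsis applies the concomitant-drug rules to both phases, so the uncovered time may be 0 days, and counting the look-backs from the first Extension dose would exclude some completers. Naming the exclusions for the Table 5 review would likewise be a helpful clarification, but its absence is missing detail.

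None of these safeguards answers the ALC point. Section 9.3.3 acts once open-label drug is running. The entry review has no stated ALC criterion to apply. The recovery times in Section 7.1 make a low count at Visit 14 less expected from the drug, which is a reason to explain it before dosing.

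**Conclusion.** The point holds in this form: neither Appendix 5 nor Section 9.3.3 withholds open-label elenbecestat from a subject whose ALC is known to be below 800/mm3 at Visit 14 or Visit 15 and has not resolved. What remains is investigator judgement on that one laboratory value; the other entry safeguards are real.

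The number affected cannot be derived, because the protocol gives no rate of low ALC in follow-up. It is probably small. The Core efficacy analysis is unaffected. The conclusion rests on two readings: that the Table 5 entries marked dd belong to Visit 15, which fits Appendix 5 calling Visit 15 Extension Day 1; and that completing treatment is not an interruption under 9.3.3. A sponsor who intended the restart rule to cover entry would need only to say so. The matter is worth correcting because the remedy is cheap and the protocol already supplies both the limit and the data.

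**What to change.** Add to the Appendix 5 eligibility criteria, and to the matching synopsis list: the first Extension dose may be dispensed only if the most recent available ALC, whether from Visit 14, Visit 15 or a later repeat, is above 800/mm3. If it is not, hold entry and use the existing 4-weekly repeats and 4-week entry window. The Visit 15 result need not be awaited when Visit 14 was normal. If it then returns low before dosing, hold the drug; if after dosing, apply Section 9.3.3.

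The cost is amendment wording and no new scheduled blood draw. A subject low at Visit 14 has repeats on about Days 785, 813 and 841. A subject first found low at Visit 15 has only the Day 841 repeat, on the last entry day, so an earlier unscheduled sample, which Section 9.1.2.2 permits when clinically indicated, may be needed to keep entry possible. A persistently low count with a confirmed non-drug cause would also bar entry; the 9.3.3 restart rule likewise makes no exception by cause. A few entries will be delayed or lost, a modest price for the long-term safety and delayed-start analyses.
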